2.8.2 Deaths

Separate summary and listing will be provided for deaths.

2.8.3 Laboratory data

The summary of laboratory evaluations will be presented for two groups of laboratory tests (hematology and serum chemistry).

The general guideline for laboratory summaries (including vital signs and ECGs in Section 2.8.4.1 and 2.8.4.2) are as below:

- all the summary of laboratory outputs (newly occurring notables, maximum changes, shift tables, by visit summary statistics) will be reported on all data collected up until end of study. Any summary presented by period will use the on-treatment definition i.e., include all assessments within last dose plus 84 days.
- all records are displayed in the listing with the on-treatment flag. i.e., occurred within last dose plus 84 days- yes or no, as well as eCRF visits and period.

Descriptive summary statistics for the change from baseline to each study visit will be presented by laboratory test and treatment group. Change from baseline will only be summarized for subjects with both baseline and post baseline values and will be calculated as:

$$\text{change from baseline} = \text{post baseline value} - \text{baseline value}$$

For laboratory test values below Lower Level of Quantification (LLQ) or above Upper Level of Quantification (ULQ) will be imputed as LLQ or ULQ value, respectively. The numerical part of the reported result will be treated as the actual LLQ or ULQ. These laboratory values will be displayed in listings using the standard unit with the reported sign (“<” or “>”).

For each parameter, the maximum change (maximum decrease and maximum increase) from baseline within treatment period will be summarized analogously.

In addition, shift tables will be provided for all parameters to compare a subject's baseline laboratory evaluation relative to the most extreme laboratory test value within a treatment period. For the shift tables, the normal laboratory ranges will be used to evaluate whether a particular laboratory test value is normal, low, or high (including category “high and low”). These summaries will be presented by laboratory test and treatment group. Subjects with abnormal laboratory values will be listed and values outside the normal ranges will be flagged. The following laboratory parameters will be analyzed with respect to numerical Common Terminology Criteria for Adverse Events (CTCAE) grades, given in Table 2-9: hemoglobin, platelets, white blood cell count, neutrophils, lymphocytes, creatinine, total bilirubin (TBL), gamma-glutamyl transferase (GGT), alanine aminotransferase (ALT), aspartate aminotransferase (AST) alkaline phosphatase (ALP) and estimated glomerular filtration rate (eGFR).

The number and percentage of subjects with CTCAE grade newly occurring or worsening after baseline will be presented. These summaries will be split into hematology and chemistry.

Table 2-11 CTCAE grades for laboratory parameters to be analyzed

CTCAE v4.0 Term	Grade 1	Grade 2	Grade 3	Grade 4
HGB decreased (Anemia)	<LLN – 100 g/L	<100 – 80 g/L	<80 g/L	Life threatening consequences; urgent intervention
Platelet count decreased	<LLN – 75.0 x10e9 /L	<75.0 - 50.0 x10e9 /L	<50.0 – 25.0 x10e9 /L	<25.0 x 10e9 /L
White blood cell decreased	<LLN - 3.0 x 10e9 /L	<3.0 - 2.0 x 10e9 /L	<2.0 - 1.0 x 10e9 /L	<1.0 x 10e9 /L
Neutrophil count decreased	<LLN - 1.5 x 10e9 /L	<1.5 - 1.0 x 10e9 /L	<1.0 - 0.5 x 10e9 /L	<0.5 x 10e9 /L
Lymphocyte count decreased	<LLN - 0.8 x 10e9/L	<0.8 - 0.5 x 10e9 /L	<0.5 - 0.2 x 10e9 /L	<0.2 x 10e9 /L
Creatinine increased	>ULN - 1.5 x ULN	>1.5 - 3.0 x ULN	>3.0 - 6.0 x ULN	>6.0 x ULN
TBL increased	>ULN - 1.5 x ULN	>1.5 - 3.0 x ULN	>3.0 - 10.0 x ULN	>10.0 x ULN
GGT increased	>ULN - 2.5 x ULN	>2.5 - 5.0 x ULN	>5.0 - 20.0 x ULN	>20.0 x ULN
ALT increased	>ULN - 3.0 x ULN	>3.0 - 5.0 x ULN	>5.0 - 20.0 x ULN	>20.0 x ULN
AST increased	>ULN - 3.0 x ULN	>3.0 - 5.0 x ULN	>5.0 - 20.0 x ULN	>20.0 x ULN
ALP increased	>ULN – 2.5 x ULN	>2.5 - 5.0 x ULN	>5.0 - 20.0 x ULN	>20.0 x ULN
eGFR	<LLN – 60ml/min/1.73m ²	<60-30 ml/min/1.73m ²	<30-15 ml/min/1.73m ²	<15 ml/min/1.73m ²

Shift tables will be presented comparing baseline laboratory result (CTCAE grade) with the worst results (expressed in CTCAE grade) during the treatment phase analyzed. Of note, baseline will be defined as last assessment prior to first dosing in treatment phase. If no pre-treatment value exists, also a value recorded after first dose can be used as baseline if it was collected on the same day as first dose, see Section 2.1.1.3.

The number and percentage of subjects with newly occurring or worsening after baseline (treatment emergent) liver enzyme abnormalities will be presented for the treatment period based on the event criteria given in Table 2-12. For pooled DMC analysis 95% confidence will be provided. Standard laboratory change from baseline tables of liver function test by visit will be produced.

Table 2-12 Liver-related events

Parameter	Criterion
ALT	>ULN; >3xULN; >5xULN; >8xULN; >10xULN
AST	>ULN; >3xULN; >5xULN; >8xULN; >10xULN
ALT or AST	>3xULN; >5xULN; >8xULN; >10xULN
TBL	>ULN; >1.5xULN, >2xULN
ALP	>ULN; >1.5xULN, >2xULN, >3xULN, >5xULN
ALT or AST & TBL	ALT or AST >3xULN & TBL >1.5xULN; ALT or AST >3xULN & TBL >2xULN; ALT or AST >5xULN & TBL >2xULN;

	ALT or AST >8xULN & TBL >2xULN
	ALT or AST >10xULN & TBL >2xULN
ALT or AST & TBL & ALP	ALP > 3x ULN & TBL > 2x ULN ALP > 5x ULN & TBL > 2x ULN ALT or AST >3xULN & TBL >2xULN & ALP <2xULN (Potential Hy's Law) (ALT or AST > 3x ULN & TBL > 2x ULN & ALP < 2x ULN) or reported Hy's Law case

For a combined criterion to be fulfilled, all conditions have to be fulfilled on the same visit. The criteria are not mutually exclusive, e.g. a subject with ALT = 6.42xULN is counted for ALT >3xULN and ALT>5x ULN.

Individual subject data listings will be provided for subjects with newly occurring or worsening abnormal laboratory data. Data of subjects with newly occurring or worsening liver enzyme abnormalities will be listed in an additional listing.

For the DMC, a panel graph will be presented to display shift from baseline to maximum evaluation for each of the liver function test (including ALT, AST, ALP and TBL) by treatment. Similarly a graphical presentation of each hematology parameter (including Leukocytes, neutrophils, lymphocytes and platelets) will be presented to display shift of baseline to minimum evaluation based on CTCAE grades.

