## Amendment 1 (25-Sep-2020)

### Amendment rationale

The rationale for the amendment is to introduce a level of flexibility in drug dispensation, protocol assessment and visit schedule if a major health care event requires it (i.e. COVID-19 pandemic) allowing patients to remain in the trial and continue treatment while being monitored for safety.

The purpose of these changes is to reduce the risk of exposure for patients and site staff and potentially the risk of transmission of infectious diseases (e.g. COVID-19).

These changes are limited to the duration of COVID-19 pandemic or of any other major health care event and must be done in accordance with the local rules and regulations relevant to pandemic containment measures.

Further to the above, minor corrections, clarifications and editorial changes were undertaken in the protocol.

Changes to the protocol:

Changes to specific sections of the protocol are shown in the track changes version of the protocol using strike through red font for deletions and red underlined for insertions.

The Amendment includes changes:

- Due to COVID-19 pandemic or any other pandemic
  - Allowing shipment of study medication to patient's home ([Section 5.5.2](#))
  - Alternative options visits ([Sections 6, 6.5, 7.1](#))
  - Local laboratory testing for safety purposes ([Section 6.5.5](#))
  - Home Pregnancy testing ([Section 6.5.8](#))
  - Remote PRO collection ([Section 6.6.1.1](#))
  - Informed Consent Form ([Section 10.2](#))
  - Home Nursing Informed Consent Form ([Section 10.2](#))
- Significant Update to Original Protocol:
  - Added Inflammatory Bowel Disease as an example for discontinuation of study treatment ([Section 5.6.2](#)).
  - ICF ([Section 10.2](#))
- To manage inconsistencies and provide clarifications in the original protocol
  - clarify prior medication ([Section 5.5.7](#))
  - correct data collection to source only (weight in IRT, [Table 6-1](#); [Table 6-2](#))
  - Imputation method ([Section 9.4.3](#))
  - Remove sensitivity analysis ([Section 9.4.4](#))
  - Add growth/weight [REDACTED] to Safety [Section 9.5.2](#)
  - As well as other miscellaneous minor corrections, modifications and text adjustments
    - Modification in Protocol [summary secondary objectives](#).

- Modification in footnote 13 of [Table 6-1](#).
- Modification in Urine pregnancy test, [REDACTED] weight in IRT and footnote 10 in [Table 6-2](#).
- Modification in [Section 9.5.4](#).
- Modification in [Section 9.6](#).

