Efficacy assessments	
Investigator's Global Assessment (IGA mod 2011)
 
Psoriasis Area and Severity Index (PASI)

Key safety assessments	
Adverse Events
 
Physical Exam
 
Vital Signs
 
Height and Weight
 
Laboratory evaluations (hematology, clinical chemistry, urinalysis)
 
ECG
 
Pregnancy and assessments of fertility

Other assessments	
Pharmacokinetics
 
Immunogenicity IG

	Children's Dermatology Life Quality Index (CDLQI)
Data analysis	PASI 75 response at Week 12 and IGA 0 or 1 response at Week 12 will be evaluated and compared to historical placebo control. The secondary variable of PASI 90 response at Week 12 will be analyzed in the same way as the primary variable. Efficacy analysis will report the Bayesian posterior of the log-odds ratio between the secukinumab treatment groups and the historical placebo control. The median, 95% CI and the probability of a positive treatment difference of the posterior logs odds ratio will be presented. The co-primary efficacy variables and secondary efficacy variables will be analyzed using the Full Analysis Set (FAS).
Key words	Pediatric, psoriasis, children, adolescents, secukinumab

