**Table 6-2      Assessment schedule - Years 2-4 (continued)**

Period	Treatment Period (years 2-4)												Follow-up Period b			Unscheduled d
Week	64	76	88	104	116	128	140	156	168	180	192	208 EOT	212	216	224 EOF	
Day	449	533	617	729	813	897	981	1093	1177	1261	1345	1457	1681	1709	1765	
Concomitant medications 	Update as necessary															x
Surgeries and non-drug procedures	Update as necessary															x
Physical Exam	S	S	S	S	S	S	S	S	S	S	S	S	s		S	S
Height 	x	x	x	x	x	x	x	x	x	x	x	x	x	x	x	x
Weight	x	x	x	x	x	x	x	x	x	x	x	x	x	x	x	x
Vital signs (BP & pulse)	x	x	x	x	x	x	x	x	x	x	x	x	x	x	x	x
Hematology 	x	x	x	x	x	x	x	x	x	x	x	x	x	x	x	x
Blood Chemistry  , Urinalysis (local)	x	x	x	x	x	x	x	x	x	x	x	x	x	x	x	x
Urine Pregnancy test (local; in females of childbearing potential) 	S	S	S	S	S	S	S	S	S	S	S	S			S	S
ECG (standard 12-lead)				x		x		x		x		x			x	x
Blood sample for IG 				x				x				x			x	x 
Blood sample for PK 				x				x				x			x	x 
PASI	x	x	x	x	x	x	x	x	x	x	x	x	x	x	x	x
IGA mod 2011	x	x	x	x	x	x	x	x	x	x	x	x	x	x	x	x
CDLQI 	x	x	x	x	x	x	x	x	x	x	x	x				x

Period	Treatment Period (years 2-4)												Follow-up Period b			Unscheduled d
	64	76	88	104	116	128	140	156	168	180	192	208 EOT	212	216	224 EOF	
Week	64	76	88	104	116	128	140	156	168	180	192	208 EOT	212	216	224 EOF	
Day	449	533	617	729	813	897	981	1093	1177	1261	1345	1457	1681	1709	1765	
(Serious) Adverse event assessment	Update as necessary															x
Data entry of weight into IRT 	x	x	x	x	x	x	x	x	x	x	x	x				
Contact IRT	x	x	x	x	x	x	x	x	x	x	x	x				
Administration of Study Drug 	x	x	x	x	x	x	x	x	x	x	x					
End of Treatment												x				
Study completion															x	

R=randomization, PK=pharmacokinetics, ECG=Electrocardiogram, CDLQI= children's dermatology life quality index, IRT=Interactive response technology,

X=assessment entered or transferred into the clinical database. S= assessment only recorded in source

aDuring EOT visit, subjects will have their last assessments performed for treatment period. This visit will also be performed for all subjects who will discontinue early the treatment period.

bFollow-up assessments are to be conducted for subjects who complete treatment period and for subjects who discontinue study treatment early

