#### **6.5.5.4 Urinalysis**

##### **Urine Dipstick (local)**

A midstream urine sample (approximately 30 mL) will be obtained, in order to avoid contamination with epithelial cells and sediments, and allow proper assessments.

A semi-quantitative ‘dipstick’ evaluation for the following parameters will be performed: specific gravity, pH, glucose, protein, bilirubin, ketones, leukocytes and blood, micro albumin.

Urinalysis will be measured locally at scheduled study visits as specified in [Table 6-1](#), [Table 6-2](#).

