### **Laboratory data**

The summary of laboratory evaluations will be presented for three groups of laboratory tests (hematology, serum chemistry and urinalysis). Descriptive summary statistics for the change from baseline to each study visit will be presented. These descriptive summaries will be presented by test group, laboratory test and treatment group. Change from baseline will only be summarized for subjects with both baseline and post baseline.

In addition, shift tables will be provided for all parameters to compare a subject’s baseline laboratory evaluation relative to the visit’s observed value. For the shift tables, the normal laboratory ranges will be used to evaluate whether a particular laboratory test value was normal, low, or high for each visit value relative to whether or not the baseline value was normal, low, or high. These summaries will be presented by laboratory test and treatment group. Shifts will be presented for most extreme values post-baseline.

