2.8.3 Laboratory data

The summary of laboratory evaluations will be presented for two groups of laboratory tests (hematology and serum chemistry).

The general guideline for laboratory summaries (including vital signs and ECGs in Section 2.8.4.1 and 2.8.4.2) are as below:

- all the summary of laboratory outputs (newly occurring notables, maximum changes, shift tables, by visit summary statistics) will be reported on all data collected up until end of study. Any summary presented by period will use the on-treatment definition i.e., include all assessments within last dose plus 84 days.
- all records are displayed in the listing with the on-treatment flag. i.e., occurred within last dose plus 84 days- yes or no, as well as eCRF visits and period.

Descriptive summary statistics for the change from baseline to each study visit will be presented by laboratory test and treatment group. Change from baseline will only be summarized for subjects with both baseline and post baseline values and will be calculated as:

$$\text{change from baseline} = \text{post baseline value} - \text{baseline value}$$

For laboratory test values below Lower Level of Quantification (LLQ) or above Upper Level of Quantification (ULQ) will be imputed as LLQ or ULQ value, respectively. The numerical part of the reported result will be treated as the actual LLQ or ULQ. These laboratory values will be displayed in listings using the standard unit with the reported sign (“<” or “>”).

For each parameter, the maximum change (maximum decrease and maximum increase) from baseline within treatment period will be summarized analogously.

In addition, shift tables will be provided for all parameters to compare a subject's baseline laboratory evaluation relative to the most extreme laboratory test value within a treatment period. For the shift tables, the normal laboratory ranges will be used to evaluate whether a particular laboratory test value is normal, low, or high (including category “high and low”). These summaries will be presented by laboratory test and treatment group. Subjects with abnormal laboratory values will be listed and values outside the normal ranges will be flagged.

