All the calculations were performed in the R package RBesT (version 1.3.1) through the meta-analytical-predictive framework ([Spiegelhalter et al. 2004](#), [Neuenschwander et al. 2010](#)).

Table 3-2 Predictive placebo response rates for this study from model of historical data

Endpoint	Mean	Standard Deviation	Median	95% Credible Interval
IGA 0 or 1	9%	6%	8%	1-23%
PASI 75	10%	6%	9%	2-25%
PASI 90	6%	4%	5%	1-18%

Based on confirmatory efficacy in the adult phase III program (CAIN457A2302, CAIN457A2303, CAIN457A2308 and CAIN457A2309), the PASI 75, IGA 0/1 and PASI 90 response rate at week 12 was assumed as 65%, 45% and 39% for secukinumab. Non-informative prior was set for secukinumab arm. A sample size of 40 pediatric patients from this

study under each high or low secukinumab arm over predictive placebo response (Table 3-2) will lead to a power of approximately 99% for each co-primary endpoint and secondary endpoint. Details as following:

- A sample size of 40 pediatric patients per treatment group and true response rates of 65% for PASI 75 and 45% for IGA mod 2011 0 or 1 response for secukinumab was assumed. For each co-primary endpoint there is approximately 99% power to detect a posterior probability of the log odds ratio difference between placebo and secukinumab to exceed with at least 97.5%.
- Similarly, for the secondary endpoint of PASI 90 response there is approximately 99% power to provide a posterior probability of at least 97.5% that the PASI 90 response rate on secukinumab is greater than placebo. This assumes a response rate of 39% for secukinumab.

4 Change to protocol specified analyses

The following are changes to protocol specified analysis:

Following HA recommendation to impute subjects with all post-baseline missing values as non-responders according to the intention to treat principal and to remain consistent with the adult studies and pediatric data used within the MAP analysis, the primary analysis will be performed on pure non-responder imputation and the MI dropped. Modified non-responder analysis may still be performed upon request from HA. No sensitivity analysis will be provided for the Bayesian analysis. For the descriptive summary of key efficacy endpoints, results using pure non-responder imputation as well as multiple imputation will be provided.

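### SAP 2.8.3 leaves urinalysis out of the laboratory summaries that Protocol 9.5.2 specifies, and SAP Section 4 does not declare the removal

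*SAP*

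**What the plan says.** Protocol 9.5.2, under Laboratory data, has the summary "presented for three groups of laboratory tests (hematology, serum chemistry and urinalysis". It asks for descriptive change from baseline by visit and treatment group, and for shift tables covering every parameter.

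SAP 2.8.3 has a parallel sentence with a different count: "The summary of laboratory evaluations will be presented for two groups of laboratory tests (hematology and serum chemistry". The wording is identical in the July 2020 and September 2023 SAPs.

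Urinalysis remains part of the trial. The protocol summary lists it among the key safety assessments: "Laboratory evaluations (hematology, clinical chemistry, urinalysis". Protocol 6.5.5.4 specifies a local, semi-quantitative dipstick covering "specific gravity, pH, glucose, protein, bilirubin, ketones, leukocytes and blood, micro albumin". In Tables 6-1 and 6-2 urinalysis shares a row with blood chemistry, and that row is marked x. The legend reads: "X=assessment entered or transferred into the clinical database. S= assessment only recorded in source".

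SAP Section 4 opens its list with "The following are changes to protocol specified analysis". Urinalysis is not among the items that follow.

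**The concern.** Clinical laboratory variables belong to a secondary safety objective (Protocol Table 2-1). The SAP narrows the protocol's plan for them by one whole test group, and does so outside the section meant to record such changes.

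What is at stake is the aggregate view. A listing lets a reader find one child's urine protein result. It does not show how many children in the low-dose and high-dose arms moved from negative to positive, or how far. The protocol's summary and shift table were meant to show that.

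**Working it through.** No sample size, power or error rate is involved. The check compares the texts and makes two counts.

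**1. Groups planned.**

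| Source | Hematology | Serum chemistry | Urinalysis | Groups |
|---|---|---|---|---|
| Protocol 9.5.2 | yes | yes | yes | 3 |
| SAP 2.8.3 (2020) | yes | yes | no | 2 |
| SAP 2.8.3 (2023) | yes | yes | no | 2 |

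The difference is 3 − 2 = 1 group, urinalysis.

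**2. Parameters affected.** Protocol 6.5.5.4 names specific gravity, pH, glucose, protein, bilirubin, ketones, leukocytes, blood and micro albumin, which makes 9.

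**3. Are the data available?** Yes. The urinalysis row is marked for database entry. In Table 6-2 the urine pregnancy test is marked S, so the protocol does separate source-only tests there, and urinalysis is not one of them.

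**4. Is the protocol text superseded?** No. Amendment 1 (25 September 2020) postdates the 2020 SAP, its change list shows an addition to Section 9.5.2 on growth and weight, and the current 9.5.2 still names three groups. The 2023 SAP came later and still names two.

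**5. Is the change declared?** SAP Section 4 covers non-responder imputation and the dropped multiple imputation, the absence of Bayesian sensitivity analyses, the Week 16 scope, the Week 24 analysis, added subgroup summaries, exposure-adjusted rates and COVID-19 reporting. It has no entry on urinalysis. The visible document-history rows have none either. Some history rows are redacted, and nothing is inferred from those.

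**6. Does another part of the SAP fill the gap?**
- The toxicity-grade summaries (Table 2-11) are divided between hematology and chemistry and contain no urine test. Table 2-12 contains liver tests only.
- The shift-table sentence in 2.8.3 refers to all parameters, but it follows the sentence that limits the section to two groups.
- SAP 2.4.1.2 uses urine protein grades to illustrate choosing the worst record in a visit window. That is a selection rule and plans no output.
- Protocol Appendix 1 has a heading that includes urinalysis but sets no urine threshold, so a notable-value table would not cover it.

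**7. What remains?** SAP 2.8.3 keeps listings of all laboratory records, and its two-group limit is placed on the summary rather than on the listings. Protocol 7.1 makes an abnormal result an adverse event when it is clinically significant, causes symptoms or needs therapy.

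**The case against.** The strongest reply is that the SAP never expressly withdraws the urinalysis analysis. Its introduction says that data are analyzed under Section 9 of the protocol, and it works with reference to a project-level standard analysis plan and output shells that are not public. Urine tables might be produced from those. The urine protein example in 2.4.1.2 and the all-parameters wording point the same way. Section 2.8.4.3 is missing from the public copy, and the 2020 document history records shift summaries added there.

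Part of this stands: the documents cannot show which tables will actually be run, and the content of 2.8.4.3 is unknown. It does not remove the conflict. A general reference to Section 9 cannot override an explicit count of two, and the urine example and the all-parameters phrase do not plan a urinalysis output.

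A second reply concerns weight. Dipstick readings are local and semi-quantitative, so the numeric change from baseline in Protocol 9.5.2 suits them poorly. Renal safety monitoring is marked not applicable, and the SAP already summarizes creatinine and eGFR by grade with shift tables. This stands. It keeps the point minor and determines the form of the fix, but it does not justify removing the group without saying so.

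**Conclusion.** The conflict holds and is minor. The protocol specifies three laboratory groups, the SAP plans two, and the removal of urinalysis is undeclared. Followed as written, the SAP leaves nine dipstick parameters with no summary by dose group and no shift table.

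This rests on two assumptions: that SAP 2.8.3 governs the laboratory outputs, and that its listing provision covers urine records.

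A reader might infer more, and the documents do not support it:
- **That urine safety signals would be lost.** Listings and adverse event reporting remain. Efficacy, dosing and case detection are unaffected.
- **That the sponsor reaffirmed three groups in Amendment 1, or removed urinalysis on purpose.** The amendment's visible change to 9.5.2 concerned growth and weight. It shows that the protocol text is current, not that the point was considered.
- **That a definite number of visits per child goes unsummarized.** The Year 1 schedule columns do not read reliably in the public copy, so no visit count is given.

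**What to change.** In SAP 2.8.3, restore urinalysis as the third laboratory group, with two outputs:
- a by-visit table of counts and percentages in each dipstick category, by treatment group;
- a baseline-to-worst shift table on the same categories.

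Use the worst-record rule in SAP 2.4.1.2 when a visit window holds more than one result. Do not use numeric change-from-baseline statistics. Specific gravity and pH can be abnormal in either direction, so for these two use low, normal and high categories, as the SAP's other shift tables do.

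If the sponsor does intend to drop the urinalysis summary, state this in SAP Section 4 with the reason.

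The cost is one or two tables from data already in the clinical database, or a short statement in Section 4. No visit, sample or procedure is added.
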